1.3. Abbreviations

AE: adverse event

CI: confidence interval

Co-PI: co-principal investigator

CR: cure rate

CRF: case report form

EPG: egg per gram

ERR: egg reduction rate

GCP: Good Clinical Practice

Hb: haemoglobin

ICH: International Council for Harmonisation

IEC: independent ethics committee

PHL-IdC: Public Health Laboratory Ivo de Carneri

PI: Principal Investigator

SAE: serious adverse event

Swiss TPH: Swiss Tropical and Public Health Institute

STH: soil-transmitted helminths

WHO: World Health Organization

1.4. Synopsis

Study title	Efficacy and safety of a new chewable tablet of mebendazole versus the swallowable, standard mebendazole tablet against hookworm infections in children: a randomized controlled trial
Short title	Efficacy of chewable and swallowable MEB tablets
Protocol number, version and date	V4.01, 26.08.2019
Trial registration	Will be registered on http://clinicaltrials.gov/
Study type	Phase 2 trial
Sample size	400
Indication	Hookworm infection
Investigational product and reference treatment	Mebendazole
Study rationale	To provide evidence on the safety and efficacy of a chewable tablet of mebendazole compared to the standard tablet in preschool- and school-aged children infected with hookworm.
Study objectives	
To compare the efficacy and safety of two formulations of mebendazole: (i) single dose of 500 mg chewable tablet, and (ii) single dose of 500 mg standard swallowable tablet of mebendazole in participants aged 3-12, inclusive, infected with hookworm.
 
The primary objective is to comparatively assess the efficacy in terms of egg reduction rates (ERRs) against hookworm infections using the duplicate Kato-Katz thick smear method on two stool samples among preschool- and school-aged children 14-21 days after the following oral treatment regimens:
 
 • 500 mg swallowable tablet of mebendazole • 500 mg chewable tablet of mebendazole

	
The secondary objectives of the trial are:
 
 • To evaluate the safety and tolerability of the two formulations • To evaluate the cure rates (CRs) of the two formulations against hookworm • To determine the CRs and ERRs against Ascaris lumbricoides and Trichuris trichiura • To investigate the acceptability and age-appropriateness of both formulation when administered to children between 3 and 12 years of age 
The exploratory objectives of this study are:
 
 • To assess how well caregivers understand the clinical trials aim, procedures, their rights, risks and potential benefits • To compare the effect of different methods of providing information on their understanding of the clinical trial
Study design	Randomized controlled, open-label, parallel-group, superiority trial (outcome assessors are blinded).
Study product / intervention	Administration of a single oral dose of a 500 mg chewable tablet of mebendazole
Comparator(s)	500 mg swallowable tablet of mebendazole
Key inclusion / exclusion criteria	
Inclusion: preschool- and school-aged children (3-12 years) with hookworm with at least two slides of quadruplicate Kato-Katz thick smears positive and infection intensities of at least 50 eggs per gram of stool (EPG), with written informed consent signed by the caregiver, able and willing to be examined by a study physician before treatment and to provide two stool samples at baseline.
 
Exclusion: pregnant, any abnormal conditions or history of major systemic or chronic illnesses, severely anaemic (Hb < 80 g/l), received anthelmintic treatment or metronidazole within the past four weeks, or is attending any other clinical trial during this

	study.
Primary endpoints	ERRs on hookworm, assessed 14-21 days post treatment
Secondary endpoints	CRs against hookworm, assessed 14-21 days post treatment CRs and ERRs against A. lumbricoides and T. trichiura Safety, assessed 14-21 days post treatment Acceptability and age-appropriateness of the tablets, assessed during treatment
Exploratory endpoints	Caregivers understanding of the clinical trial in general and by caregiver group, assessed during the informed consenting procedure
Interim analyses	None
Study duration	12 weeks total; up to 10 weeks per participant
Schedule	02/2019 of first-participant in (planned) 05/2019 of last-participant out (planned)
Study site	Wawi, Mvumoni, Bwagamoyo, Piki and Mzambarauni schools, Pemba, Tanzania
Measurements & procedures	A first stool sample will be collected and if the participant is found positive for hookworm a second stool sample will be requested, if possible the next day. The medical history of the participating individuals will be assessed with a standardized questionnaire contained in the case report form, in addition to a clinical and physical examination carried out by the study physician before treatment. This examination also includes pricking subjects' fingers to measure haemoglobin (Hb) levels and, in the case of female participants aged ≥ 10 years, a urine pregnancy test. Randomization of participants into the two treatment arms will be stratified according to intensity of infection. Participants will be interviewed before treatment for clinical symptoms and 3, and 24 hours after treatment to assess occurrence of adverse events (AEs). The efficacy of the treatment will be determined 14-21 days post-treatment by

	
collecting another two stool samples. All stool samples will be examined with duplicated Kato-Katz thick smears for hookworm, A. lumbricoides and T. trichiura eggs.
 
During treatment, a sheet will be filled out for each participant to record his/her behaviour during the process of swallowing the tablet. School-aged children will be asked a few questions about their receptivity and the adequacy of the formulation of mebendazole they received, immediately after treatment.

Statistical analyses	
The primary analysis will use the full analysis set (available case population) according to the intention to treat principle defined as all randomized subjects which provide any follow-up data. Only subjects which were negative at baseline and erroneously randomized will be excluded from the analysis. Because palatability and ease of swallowing are critical attributes in children; therefore, a per-protocol analysis will be conducted additionally to disentangle drug efficacy from adherence effects.
 
Geometric mean egg counts will be calculated for the different treatment arms before and after treatment to assess the corresponding ERRs. Bootstrap resampling with 5,000 replicates will be used to calculate 95% confidence intervals (CIs) for ERRs and the difference between the two ERRs.
 
Differences in CRs will be assessed using unadjusted logistic regressions. In a subsequent analysis an adjusted logistic regression (adjustment for age, sex, weight and strata) will be performed.

GCP statement	
This study will be conducted in compliance with the protocol, the current version of the Declaration of Helsinki, ICH-GCP E6 as well as all national legal and regulatory requirements.

Key explanation for the inclusion of children	
This study will be carried out in children since infection with hookworm and other soil-transmitted helminths occurs most often in this age group and they will be the population group treated with the new formulation.

Recruitment procedure	
This school-based trial will be carried out in five primary schools with kindergarten (Wawi, Mvumoni, Bwagamoyo, Piki and

	Mzambarauni) on Pemba Island, Tanzania.
Coverage of damages	Winterthur Police Nr. 4746321, National Insurance Cooperation of Tanzania LTD, GTA No: 00062.

Soil-transmitted helminthiases are caused by one of the three soil-transmitted helminths (STH), *Ascaris lumbricoides*, *Trichuris trichiura* and hookworm (*Ancylostoma duodenale* and *Necator americanus*). Currently, STH still infect about two billion people worldwide, mostly in tropical and subtropical regions [1]. The global burden of STH infections reached over three million disability-adjusted life years in 2016 [2]. Children living in less developed settings, with crowded living conditions, inadequate sanitation and the lack of access to clean water, harbour the most intense infections [3-6]. These diseases can cause considerable burden including dietary deficiencies, anaemia, physical and cognitive retardation in children and reduction in work performance in adulthood [4, 7-10]. Currently, the main strategy to control STH infections is preventive chemotherapy which consists on the regular administration of either mebendazole (500 mg) or albendazole (400 mg) to children living in regions where these parasites are highly prevalent (WHO 2017). Preventive chemotherapy is promoted by the World Health Organization (WHO), due to its simple implementation and strong impact on morbidity by decreasing worm burden. WHO aims at reducing the prevalence of moderate and heavy STH infections in preschool and school-aged children to below 1% by 2020 [11]. However, there is a lack of appropriate paediatric formulations against soil-transmitted helminths; the mebendazole tablets currently used in mass drug administration programmes are solid (swallowable), which may make them inappropriate for younger age groups to swallow.

The European Medicines Agency recommends swallowable tablets for children aged 6 years or older [12] and the WHO recommends only administering chewable tablets to children aged 5 or younger [13]. Indeed, in the UK, children aged 6 years and older are willing to take tablets of any size (Ranmal et al 2016). However, children as young as 3 years old have been found to easily swallow conventional tablets [14-16] and children above 6 years of age have reported difficulties [17]. A survey in Nigeria found that caregivers prefer liquid formulations because they are sweet and do not require further preparation (Orubu et al 2017). However, solid tablets have significant advantages: they have a lower risk of incorrect administration (Walsh et al 2011) and are easily stored, transported and distributed (WHO 2012). In low-resource settings, as are most of those requiring preventive chemotherapy, the ease of storage, transport and distribution of the drugs is particularly important. Thus, ideally, a formulation which could be transported and stored in a solid form but administered in a semi-solid or liquid form could be a solution for young children.

The WHO's call for a more child-friendly formulation of mebendazole resulted in the development of a chewable 500 mg tablet by Johnson & Johnson (Vermox™). In the case of young children, the WHO recommends crushing the tablet on a spoon, adding 2-3ml of clean

water and waiting for two minutes until it becomes a soft mass with semi-solid consistency which can more easily be administered. On the other hand, WHO recommends that older children should be encouraged to chew it (but never swallow it whole). Randomized, double-blind, placebo-controlled trials which took place in Ethiopia and Rwanda have established safety and effectiveness against *A. lumbricoides* and *T. trichiura* in children aged 1-16 years [18, 19]. The efficacy of this chewable tablet of mebendazole against hookworm has not yet been studied. This formulation aims at making it easier for pre-school and school-aged children (PSAC and SAC) to swallow the drug but its acceptability has not yet been explored. Thus, in this study we will compare the efficacy, safety, and acceptability and age-appropriateness of the two tablets (swallowable and chewable) of mebendazole and explore caregivers' perceptions about both formulations.

3. Trial objective and purpose

The overall goal of this study is to determine if a chewable formulation of mebendazole is superior to a swallowable formulation tablet of mebendazole (standard of care) against hookworm in children.

We hypothesize that the chewable formulation of mebendazole has a higher efficacy against hookworm infections than the swallowable one. Better absorption and bioavailability as well as better palatability are expected to contribute to superior efficacy.

The **primary objective** of the study is to compare the egg reduction rates (ERRs) of two different mebendazole formulations against hookworm in children (3 - 12 years old): (i) 500 mg of a single chewable mebendazole tablet and (ii) 500 mg of a single solid mebendazole tablet.

The **secondary objectives** of the trial are:

- To evaluate the safety and tolerability of the two formulations
- To evaluate the CR of the two formulations against hookworm
- To determine the CRs and ERRs against *Ascaris lumbricoides* and *Trichuris trichiura*
- To investigate the acceptability and age-appropriateness of both formulation when administered to children between 3 and 12 years of age

The **exploratory objectives** of this study are:

- To assess how well caregivers understand the clinical trials aim, procedures, their rights, risks and potential benefits

- To compare the effect of different methods of providing information on their understanding of the clinical trial

4. Methodology

4.1. Primary and secondary endpoint

The **primary endpoint** of the study is the ERRs of these two formulations of mebendazole against hookworm assessed before and 14 to 21 days post-treatment using the duplicate Kato-Katz technique. **Secondary endpoints** are the CR against hookworm, CRs and ERRs against *A. lumbricoides* and *T. trichiura* (assessed 14-21 days post-treatment), safety (assessed 3 and 24 hours post-treatment), and acceptability and age-appropriateness of the two formulations of mebendazole (assessed during treatment). **Exploratory endpoints** are how well caregivers understood the clinical trial's informed consent form and its content, and which of the informing methods increase caregivers understanding the most (assessed during the informed consenting process).

4.2. Type of trial

Randomized controlled, open-label, parallel-group, superiority, phase 2 trial.

Participants found to be positive for hookworm and eligible (hookworm eggs per gram of stool (EPG) > 100 and more than one slide with hookworm eggs), will be invited for the physical and clinical examination day which will either take place the day before treatment or on the treatment day itself, but before treatment. All invited subjects will visit one of the study physicians and nurses to undergo a physical examination. Participant's medical history, haemoglobin levels (using HemoCue), and, in the case of female participants, a pregnancy test (girls aged ≥ 10 years will be asked to provide a urine sample) will be recorded. Severely anaemic participants (below 70 g/l Hb in children aged 6-59 months and below 80 g/l Hb in children aged 5-12 years, according to WHO definition) and pregnant girls will be excluded.

Pregnant participants will be given the option of receiving a similar looking tablet which does not contain any drug to avoid any stigmatization and severely anaemic participants will receive the combination of ivermectin and albendazole (according to WHO recommendations).

4.3.2. Kato-Katz slide reading quality control

To ensure quality of hookworm diagnosis, 10% of the samples will be divided into two stool containers; one of the containers will keep its original participant ID, whereas the second container will be labeled with a new ID (assigned by the co-PI). Duplicate Kato-Katz will be prepared from both containers and the findings compared. For hookworm, results are considered correct if no difference in presence/absence is found. In the case of *A. lumbricoides* and *T. trichiura*, 10% of slides will be re-read by another laboratory technician. Results are considered correct if the following tolerance margin is not exceeded: egg counts are +/-10 eggs for counts ≤ 100 eggs or +/-20% for counts > 100 eggs (for each species separately) [25]. In case discrepancies above the tolerance margin are noted in one or more slides, these slides will be re-read by the local technicians. The new results will be discussed, so that in case of discordant results, slides can be re-evaluated to reach consensus. All microscopically analysed quadruplicate Kato-Katz thick smears will be destroyed within one day after passing the quality control.

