4.3.3. Assessment of efficacy after treatment

The efficacy of the treatment in participants will be determined 14-21 days post-treatment by collecting another two stool samples, which will be microscopically examined for STH using duplicate Kato-Katz thick smears, creating a total of four slides for this time point assessment. Participants will be considered hookworm cured if no eggs were found in the follow-up stool samples.

EPG will be assessed by adding up the egg counts from the quadruplicate Kato-Katz thick smears and multiplying this number by a factor of six. Geometric and arithmetic mean egg counts will be calculated for the two treatment arms before and after treatment to assess the corresponding ERRs. Individuals will not be included in the trial if the hookworm EPG < 100 (total of the four slides) and/or if there is only one Kato-Katz thick smear slide with a hookworm egg.

Once all follow-up samples have been analysed, all participants who were still found STH-positive will receive albendazole (400 mg single dose) and ivermectin (200 $\mu\text{g}/\text{kg}$), which is currently recommended against STH by the WHO's Essential Medicines List.

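### For A. lumbricoides and T. trichiura, the slide re-read tolerance in 4.3.2 accepts a disagreement of 0 versus 1 to 10 eggs as correct, although the secondary cure rates depend on zero versus non-zero.

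*Combined protocol and SAP*

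**What the plan says.** Section 4.3.2 sets two separate quality-control rules.

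- **Hookworm.** A tenth of the samples are split into two containers, slides are made from both, and the findings are compared: "For hookworm, results are considered correct if no difference in presence/absence is found".
- **A. lumbricoides and T. trichiura.** Here "10% of slides will be re-read by another laboratory technician". The criterion is "Results are considered correct if the following tolerance margin is not exceeded", and the margin is "egg counts are +/-10 eggs for counts ≤ 100 eggs or +/-20% for counts > 100 eggs (for each species separately".

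Further reading follows only when the margin is exceeded: "In case discrepancies above the tolerance margin are noted in one or more slides, these slides will be re-read by the local technicians". Results that remain discordant are settled by consensus. Sections 4.3.2 and 7.4 have slides destroyed within a day of passing quality control (4.3.1 allows a few days). Section 7.4 has each stool sample destroyed once its duplicate slides are prepared.

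Section 4.1 lists as secondary endpoints "CRs and ERRs against *A. lumbricoides* and *T. trichiura* (assessed 14-21 days post-treatment". Section 4.3.3 defines cure in words written for hookworm: "Participants will be considered hookworm cured if no eggs were found in the follow-up stool samples". No section adds a presence/absence check for the other two species.

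**The concern.** A cure rate uses one property of a slide set: whether any egg was seen. For A. lumbricoides and T. trichiura the quality control tests a different property, closeness of counts. Near zero its margin is wide enough to ignore the one that matters. Two technicians can disagree on whether a slide is positive at all, and the plan calls the result correct.

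Three features make this more than a matter of taste.

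- The disagreement has already been found when it is passed over, so acting on it needs no new sampling.
- The plan does not say which of two readings within tolerance goes into the database. A cured or not-cured status could therefore rest on an unstated choice.
- Once the slide has passed it is soon destroyed and the stool is already gone, so the disagreement cannot be resolved later.

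At stake are the secondary cure rates for the two species and, to a lesser degree, their ERRs. Section 8.3 computes ERRs from log(EPG + 1), which is steepest near zero.

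**Working it through.** **Inputs**

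- Margin: 10 eggs when counts are at most 100; a pair passes if the margin is not exceeded (4.3.2).
- Share of slides re-read: 10% (4.3.2).
- Four follow-up slides per child; EPG = 6 × total eggs on the four slides (4.3.3).
- ERRs use log(EPG + 1) (8.3).
- Assumption: cured means no eggs on any follow-up slide, carried over from the hookworm definition.
- Assumption: 4.3.2 applies at follow-up as well as baseline; it names no time point.

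**Step 1: which zero-versus-positive pairs pass.** With readings 0 and b, the difference is b. It passes if b ≤ 10.

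- b = 1, 2, ..., 10: passes, so ten pairs.
- b = 11: 11 > 10, the first to fail.

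Both readings are below 100 in all these pairs, so the 20% branch never applies.

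**Step 2: what one such slide can do when the other three are negative.**

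| Reading | EPG | log(EPG + 1) | Status |
|---|---|---|---|
| 0 | 6 × 0 = 0 | ln 1 = 0 | cured |
| 1 | 6 × 1 = 6 | ln 7 = 1.95 | not cured |
| 10 | 6 × 10 = 60 | ln 61 = 4.11 | not cured |

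These are values for one child, not effects on an arm's cure rate or ERR.

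**Step 3: when another slide is positive.** Suppose one other slide has 1 egg. The two readings give 6 × (1 + 0) = 6 EPG and 6 × (1 + 10) = 66 EPG. The child is not cured either way, so the cure rate does not move.

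**Step 4: reach.** Let h be the share of children infected with the species whose status hinges on one slide that two technicians would read as 0 and as 1 to 10 eggs. The documents give no value for h. Re-reading 10% of slides exposes about 0.10 × h. Purely as an assumed range:

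- h = 5%: 0.10 × 5% = 0.5%.
- h = 10%: 0.10 × 10% = 1%.

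Under these assumptions, resolving the exposed disagreements would move a cure rate by at most about 0.5 to 1 percentage point. The shift would be smaller if corrections ran in both directions.

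**Step 5: after the fix.** With presence/absence agreement also required, none of the ten pairs in step 1 passes; all go to re-reading.

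**The case against.** The strongest reply is that the consequence is small. Ninety per cent of slides get no second reading under any rule, so a stricter criterion cannot repair the cure rates as a whole. One slide matters to cure only when three others, spread over two stool samples, are negative. The outcomes are secondary, in non-target species, among whichever children are co-infected, and the sample size in 8.2 does not rest on them. All of this stands and limits the weight of the point.

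It can also be said that the two quality-control rules need not match. Hookworm control compares new slides from a split sample, while the other species have the same slide read twice. The difference is therefore not in itself an inconsistency, and the margin comes from a cited source. That stands too. The point rests on the mismatch between the margin and a zero/non-zero endpoint, and a citation does not change which pairs the rule passes.

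Three stronger readings are tempting but not supported:

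- **The first reading stands.** A reader might infer this, but the plan is silent on which reading is kept.
- **The comparison between arms is biased.** Outcome assessors are blinded according to the synopsis, and the same rule applies to both arms. Nothing in the documents shows a differential error. Each arm's own cure rate can still be affected.
- **Children's further treatment is decided by these slides.** Section 4.3.3 says "all participants who were still found STH-positive will receive albendazole" plus ivermectin, so any species qualifies. The hookworm cure rates simulated in 8.2 are 10% and 20%, which leave 100 − 10 = 90% and 100 − 20 = 80% positive through hookworm alone. The tolerance could matter only among the remaining 10 to 20%, and only when a re-read slide is both the sole positive and discordant.

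**Conclusion.** The point holds in a limited form. As written, 4.3.2 certifies ten zero-versus-positive disagreements as correct for A. lumbricoides and T. trichiura, triggers no further reading, and leaves the recorded value undefined. That does not suit secondary endpoints that depend on whether any egg is present.

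Its size cannot be established from the documents. They give no distribution of follow-up counts, no frequency of low-count disagreement and no number of co-infected children. That low counts are common after treatment is plausible but not stated. The primary hookworm ERR and the hookworm cure rate fall under a separate rule and are not affected. A reader should not infer that the trial's conclusions are threatened. This is an inexpensive correction to a sampling check, worth making because the information is already in hand and is soon lost.

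The conclusion rests on two readings of the plan: that cure for these species means no eggs, and that 4.3.2 covers follow-up slides.

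**What to change.** In 4.3.2, state that a re-read A. lumbricoides or T. trichiura slide passes only if the two readings agree on presence/absence and the counts lie within the existing margin. Send any zero-versus-positive disagreement to the consensus re-reading already described, before the slide is destroyed, and record the consensus result. In the same edit, say which reading is recorded when two positive counts differ within the margin.

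The cost is a sentence or two of text and a few more slides re-read among the 10% already selected. The margin, the sampling fraction and the hookworm procedure stay as they are.
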